# 2. OBJECTIVES AND ENDPOINTS

This *8*-year study will evaluate the safety, tolerability, pharmacokinetics, and PD effects of ocrelizumab in children and adolescents ages  $\geq$  10 to < 18 years with RRMS. The data from this study will serve to determine the dosing regimen of ocrelizumab to be further investigated in the subsequent Phase III study in children and adolescents. In addition, new emergent data (e.g., Real World Evidence data) may be used to support the dose selection. Specific objectives and corresponding endpoints for the study are outlined below.

Primary Pharmacokinetic Objective	Corresponding Endpoint
To characterize the ocrelizumab PK profile in children and adolescents	Serum concentration of ocrelizumab at specified timepoints
Primary Pharmacodynamic Objective	Corresponding Endpoint
To evaluate relationship between drug exposure and PD (CD19+ B-cell	Levels of CD19+ B-cell count in blood
count) in children and adolescents	
Secondary Safety Objective	Corresponding Endpoints
To evaluate safety of ocrelizumab in children and adolescents	Occurrence and severity of adverse events, with severity determined according to NCI CTCAE v5.0
	Change from baseline in vital signs
	Change from baseline in clinical laboratory test results
	• Level of circulating B cells, T cells, natural killer cells, and other leukocytes
	• Developmental milestones (e.g., growth, bone age, age at menarche, Tanner staging)
	
 
Non–MS CNS pathology as measured by brain MRI scans
 

	
 
Levels of blood immunoglobulins
 

	
 
Antibody titers against standard vaccines
 

Secondary Immunogenicity Objective	Corresponding Endpoint
To assess ADA development to ocrelizumab	• Presence of ADAs during the study relative to the presence of ADAs at baseline
Exploratory Objective	Corresponding Endpoints
To evaluate exploratory parameters	
 
Nature, frequency, and severity of clinical and protocol–defined relapses
 

	Change in EDSS
	Change in total number of new and/or enlarging T2     hyperintense lesions
	Total number of T1 gadolinium–enhancing lesions at Week 12
	Change in Symbol Digit Modalities Test
	Change in low-contrast visual acuity

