# 3.1.1.4 *104*-Week Safety Follow-Up Period (Including B-Cell Monitoring Period, if Required)

Patients completing the 288–week treatment period or patients who discontinue treatment prematurely for any reason at any time during the study will enter the SFU period.

The SFU period will last for at least 104 weeks starting from the date of the last infusion of ocrelizumab. However, patients whose peripheral blood B cells remain depleted will continue to be monitored until their B–cell counts have returned to baseline level or to the LLN range (whichever is lower) (see Figure 2).

The decision to initiate an alternative treatment for MS during this SFU period will be at the discretion of the treating investigator.

A dedicated SFU visit (scheduled or unscheduled) directly prior to the start of an alternative MS treatment is required in order to assess the patient's clinical status and safety. Information about the alternative treatment, such as dose, route, and frequency, will be recorded on the electronic case report form (eCRF).

Patients who receive MS therapies that may change B-cell levels during the SFU period will not be entered into the prolonged B-cell monitoring period thereafter.

Because sufficient data are not available to inform risks associated with switching to other products, caution is advised while patients remain B cell depleted.

Because of the unknown safety risk of administering DMTs for MS after discontinuation of ocrelizumab, certain treatments for MS such as lymphocyte–depleting agents or lymphocyte–trafficking blockers (e.g., alemtuzumab, natalizumab, fingolimod, dimethyl fumarate, cyclophosphamide, azathioprine) are strongly discouraged for as long as the patient remains B cell depleted on account of unknown effects on the immune system (e.g., increased risk, incidence, or severity of infection).

SFU visits will be performed at 12–week intervals starting from the date of the patient's last visit (e.g., withdrawal from treatment visit or Week 288 visit). For sites where mobile nursing (MN) is used, SFU visits can alternate between site visits and MN visits for the patient's convenience.

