#### 4.5.10 Bone Age Assessment: Wrist/Hand Radiographs

Bone age should be assessed by obtaining one combined standard posterior-anterior radiograph of the left wrist and hand. The radiographs should be obtained within 4 weeks of baseline and repeated yearly ( $\pm$ 4 weeks).

If evidence of growth-plate fusion is not demonstrated at baseline but during subsequent X-rays, no further hand/wrist X-rays will be necessary provided that final growth/bone maturation has unequivocally been reached.

It is recommended that bone age be reported according to the Greulich and Pyle Atlas (Greulich and Pyle 1959); however, the practice may vary between institutions. In any case, the grading system used should be referenced on the eCRF.

This radiographic assessment will be contingent on IRB/EC approval, written informed consent from the patient's parents/guardian, and patient assent (where possible). If a site's IRB/EC does not approve the radiographic assessment, this section will not be applicable.

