- r Tanner staging assessment will be contingent on IRB/EC's approval and written informed consent from the patients' parents/legal guardian and with patient assent (as applicable). Tanner staging will be documented on the eCRF at baseline. During the study conduct, patients will have their Tanner stages documented or assessed yearly until they reach Stage 5 (see Section 4.5.8).
- s Wrist/Hand X-ray: This radiographic assessment will be contingent on IRB/EC's approval and written informed consent from the patients' parents/legal guardian and with patient assent (as applicable). One combined standard PA radiograph of the left wrist and hand will be obtained within 4 weeks of baseline and repeated yearly (± 4 weeks). If evidence of growth-plate fusion is not demonstrated at baseline but during subsequent X-rays, no further hand/wrist X-rays will be necessary provided that final growth/bone maturation has unequivocally been reached (see Section 4.5.10).
- t If a prior X-ray was obtained within the last 6 months before the WD visit, the X-ray should not be repeated.
- u "Baseline" MRI scan should be performed after the screening visit, but at least 10 days prior to the baseline visit. Baseline and Week 12 (± 2 weeks) MRI scans will be performed without a Gd-contrast agent at Week 24 (a window of minus 4 weeks can apply) and Weeks 48, 72, 96, 144, 192, 240, and 288 (window of ± 4 weeks of these scheduled visits). Also, MRI scans will be obtained in patients withdrawn from the treatment period (at a withdrawal from study visit), if not performed during the last 4 weeks.
- v Neurological examination and EDSS: See Sections 4.5.14 and 4.5.15.
- w Concomitant medications: See Section 4.4.
- x Adverse events: See Section 5.
- y Sensitive thyroid-stimulating hormone will be tested at screening and during the treatment period as indicated. Thyroid autoantibodies will be assayed only at screening.

- z Hepatitis screening and monitoring: All patients must have negative HbsAg and negative HepCAb screening test results prior to enrollment. If total HbcAb is positive at screening, HBV DNA measured by PCR must be negative to be eligible. For those patients enrolled with negative hBsAg and positive total HbcAb, HBV DNA (PCR) must be repeated every 12 weeks during the treatment period.
- aa To be completed on Visit 9 if not done at Visit 8.

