### Table 3 Safety Follow-Up (including Prolonged B-Cell Monitoring if Required) (cont.)

Note: Marks in parentheses are optional and may be done as appropriate (e.g., if needs to be repeated).

a SFU will be carried out for at least 104 weeks starting from the date of last infusion of ocrelizumab.

Visits will be performed at 12-week intervals starting from the date of the patient's withdrawal from treatment visit or from the date of the Week 288 visit. At applicable sites, site visits will alternate with mobile nursing visits. SFU applies to study patients who have completed the treatment period (i.e., up to Week 288) and to patients who withdraw early from treatment. If B cells have returned to normal levels at the end of this SFU period, then the last scheduled SFU visit will become the end-of-observation visit, and the patient will have completed the study. Patients who receive alternative MS therapies that may change B-cell levels will only be followed up for a period of *104* weeks; they will not be entered into the prolonged B-cell monitoring period thereafter. A dedicated SFU visit directly prior to the start of an alternative MS treatment is required in order to assess patient's clinical status and safety.

- b Patients whose B cells have not returned to normal levels after *104* weeks of SFU will continue with site visits every 24 weeks (± 7 days) until B-cell repletion. Once B cells have returned to normal levels, patient will be scheduled for an end-of-observation visit, and the patient will have completed the study. Patients who begin during the prolonged B-cell monitoring period, alternative MS therapies that may change B-cell levels will only be followed up until the point they initiate this alternative MS therapy; an end-of-observation visit will be scheduled, and patients will have completed the study.
- c Urine β-hCG (sensitivity of at least 25 mlU/mL) test will be performed until 24 weeks after the last dose of ocrelizumab. Female patients of childbearing potential (e.g., in Tanner stages ≥ 2 or post-onset of menarche) must agree to remain completely abstinent or to use reliable means of contraception for 24 weeks after the last dose of ocrelizumab as described in Section 5.1.5). Confirmation by a serum pregnancy test will be performed for positive urine pregnancy test.

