### Table 3 Safety Follow-Up (including Prolonged B-Cell Monitoring if Required) (cont.)

- j Patients will have their Tanner stages documented or assessed yearly until they reach Stage 5. Afterwards no further hand/wrist X-rays will be necessary provided that final growth/bone maturation has unequivocally been reached (see Section 4.5.10). For patients who have discontinued from treatment early and did not have a yearly X-ray (because the last one was performed within the last 6 months before that WD visit), an X-ray may have to be performed at the SFU Week 24 visit. From this point, subsequent X-rays will be performed yearly.
-  Brain MRI scans will be performed without a Gd-contrast agent with a window of ± 4 weeks of a scheduled visit. MRI scans will be obtained in patients withdrawn from the SFU period (at a withdrawal from SFU visit), if not performed during the last 4 weeks. *MRI scan at SFU Week 104 may be acquired if clinically indicated*. For patients who begin an alternative treatment for MS during the SFU period or while in the B-cell monitoring period, an MRI scan will be performed within the time window of 1 month prior to the start of the alternative MS treatment (unless MRI has already been performed within prior 8 weeks).
- m A telephone interview will be performed by site personnel every 4 weeks (± 6 days) between visits until 104 weeks after the last infusion to identify and collect information on any changes in the patient's health status that warrant an unscheduled visit (including new or worsening neurological symptoms, signs of infection). If prolonged B-cell monitoring is required beyond 104 weeks after the last infusion, telephone interviews will be done every 12 weeks (± 6 days) between visits.
- n For patients who undergo an alternative MS treatment while in B-cell monitoring period, telephone interview will continue to be performed every 4 weeks.
- Unscheduled site or mobile nursing visit: Assessments performed at unscheduled visits will depend on the clinical needs of the patient. All patients with new neurological symptoms suggestive of relapse should have EDSS performed within 7 days of the onset of the relapse. Other tests/assessments may be done as appropriate.

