- k Two radiographs; one combined standard PA radiograph of the left wrist and hand and a similar combined radiograph of the right wrist and hand will be obtained yearly ± 4 weeks until evidence of growth-plate fusion is demonstrated.

Male puberty stage:

Stages Description:

Stage 1 Preadolescent. Testes, scrotum, and penis are about the same size and

proportion as those in early childhood.

**Stage 2** Scrotum and testes have enlarged, and there is a change in the texture of scrotal skin and some reddening of scrotal skin.

Stage 3 Growth of the penis has occurred, at first mainly in length but with some

increase in breadth. There has been further growth of the testes and the scrotum.

Stage 4 The penis is further enlarged in length and breadth, with development of glans.

The testes and the scrotum are further enlarged. There is also further

darkening of scrotal skin.

Stage 5 Genitalia are adult in size shape. No further enlargement takes place after

stage 5 is reached.

Female puberty stage:

Stages Description:

Stage 1 Preadolescent; only papillae are elevated.

**Stage 2** Breast bud and papilla are elevated and a small amount is present; areola diameter is enlarged.

Stage 3 Further enlargement of breast mound, increased palpable glandular tissue.

Stage 4 Areola and papilla are elevated to form a second mound above the level of the rest of the breast.

Stage 5 Adult mature breast; recession of areola to the mound of breast tissue,

rounding of the breast mound, and projection of only the papilla are evident.

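### Safety follow-up schedule calls for yearly X-rays of both hands, while Section 4.5.10 defines the bone-age assessment as one left-hand image

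*Combined protocol and SAP*

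**What the plan says.** Section 4.5.10 says bone age is assessed by "obtaining one combined standard posterior-anterior radiograph of the left wrist and hand", within 4 weeks of baseline and then yearly. It sets no end by study period. It adds a condition: "This radiographic assessment will be contingent on IRB/EC approval", together with parental consent and, where possible, the patient's assent.

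The schedules for dose exploration (Appendix 1, Table 1, footnote s) and for the extension (Tables 2a and 2b, footnote n) repeat the same rule: "One combined standard PA radiograph of the left wrist and hand will be obtained within 4 weeks of baseline and repeated yearly".

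Table 3 covers safety follow-up and prolonged B-cell monitoring. Its footnote k reads differently: "Two radiographs; one combined standard PA radiograph of the left wrist and hand and a similar combined radiograph of the right wrist and hand", to be taken yearly (±4 weeks) until growth-plate fusion is shown. Elsewhere the X-ray text in Table 3's footnotes refers back to the main text: "no further hand/wrist X-rays will be necessary provided that final growth/bone maturation has unequivocally been reached (see Section 4.5.10".

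The endpoint served is in the secondary safety list in Section 2: "Developmental milestones (e.g., growth, bone age, age at menarche, Tanner staging".

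**The concern.** Two current instructions for one procedure disagree on how many images to take and of which hand. Section 4.5 requires every activity in the Appendix 1 schedule to be performed and documented, and Section 9.2 requires deviations to be documented and explained. A site that takes one image therefore departs from footnote k, and a site that takes two departs from Section 4.5.10.

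What is at stake is exposure rather than inference. Because footnote k applies until fusion, the patients who would receive the second image are skeletally immature. The plan assigns that image no use. The conflict also leaves ethics committees and families unsure what they are approving in follow-up, since Section 4.5.10 ties approval, consent and assent to an assessment it describes as a single left-hand radiograph.

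**Working it through.** The plan gives no figure to reproduce, so the check is a comparison of every wrist/hand X-ray instruction.

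| Place | Period governed | Images per occasion | Side |
|---|---|---|---|
| Section 4.5.10 | No limit stated | 1 | Left |
| Table 1, footnote s | Dose exploration | 1 | Left |
| Table 2a, footnote n | Extension, Weeks 36 to 180 | 1 | Left |
| Table 2b, footnote n | Extension, Weeks 190 to 288 | 1 | Left |
| Table 3, footnote k | Safety follow-up and B-cell monitoring | 2 | Left and right |

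1. **Where the conflict lies.** Section 4.5.10 and footnote k both apply in follow-up, because Table 3's own X-ray text cites Section 4.5.10. The difference is 2 − 1 = 1 image per occasion. Tables 1, 2a and 2b govern earlier periods. They do not contradict footnote k, but they show that the right-hand image first appears in follow-up.

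2. **Whether Section 4.5.10 can be read as bilateral.** It cannot. It uses the plural when giving the timing, but the preceding sentence specifies one left image, so the plural refers to the yearly repeats.

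3. **Whether the right-hand image has a use.** The endpoint is bone age, with no left-right comparison. Section 6 describes no analysis of it. The number of right-hand images planned at baseline or on treatment is 0. The Version 10 rationale covers longer follow-up and the exposure-period definition and does not mention bilateral imaging.

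4. **Whether the bone-age endpoint is affected.** It is not. Footnote k still includes the left image, so the series begun at baseline continues.

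5. **Why no cumulative count is given.**
   - Section 3.1.1.4 states: "The SFU period will last for at least 104 weeks starting from the date of the last infusion of ocrelizumab". For a patient who completes treatment, the last infusion is at Week 264, so follow-up ends at 264 + 104 = Week 368, which is 368 − 288 = 80 weeks after the Week 288 visit. Table 3 instead counts visits from the Week 288 or withdrawal visit, which gives 288 + 104 = Week 392.
   - The X-ray marks at follow-up Weeks 24, 48, 72 and 96 are in parentheses, and Table 3 says: "Marks in parentheses are optional and may be done as appropriate (e.g., if needs to be repeated". Week 104 has no X-ray mark.
   - The entries for prolonged B-cell monitoring (yearly) and for end of observation or withdrawal from follow-up are not in parentheses.

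6. **Ages at entry to follow-up, using 52.18 weeks per year.**
   - The youngest permitted entrant, leaving treatment at Week 24: 10 + 24/52.18 ≈ 10.5 years.
   - The youngest patient completing Week 288: 10 + 288/52.18 ≈ 15.5 years.
   - The upper bound at Week 288, since entry is below 18: 18 + 288/52.18 ≈ 23.5 years.

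**The case against.** The strongest reply is that this is a drafting slip with little consequence. The X-ray needs ethics approval, parental consent and patient assent. It stops at fusion, and the marks from Week 24 to Week 96 are optional. Patients who complete Week 288 are about 15.5 to 23.5 years old, so many may already be fused; the 10.5-year-old is a worst case. The number exposed is unknown and may be small. All of this stands and limits the size of the point. It does not remove the conflict: footnote k itself is worded as mandatory, and the prolonged-monitoring and end-of-observation entries are not optional.

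Two narrower replies concern the right-hand image. Section 4.5.10 recommends reading bone age against a published atlas, so a right-hand film could be judged for fusion without an earlier film of the same hand. That is fair, and the missing baseline carries less weight than the missing purpose. Footnote k also links both images to growth-plate fusion. That is a rule for when to stop, not a reason to image a second hand.

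Finally, one may ask which text is intended. Section 4.5.10 and three of the four schedule footnotes say left only, which makes left only the likely intent, but the sponsor should confirm it.

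**Conclusion.** The concern holds. Footnote k of Table 3 contradicts Section 4.5.10 on the same follow-up X-ray, and nothing in the documents reconciles them or gives the right-hand image a purpose. The size is one extra image per follow-up X-ray occasion, confined to patients with unfused growth plates and with approval, consent and assent in place. This rests on the text alone; no assumption is made about how many patients reach follow-up unfused or about radiation dose. The bone-age endpoint, PK, PD and dose selection are unaffected. It should be corrected because it concerns unexplained imaging of patients who may be minors, but it does not threaten the trial's conclusions.

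**What to change.** Reword Table 3 footnote k to specify one combined posterior-anterior radiograph of the left wrist and hand, yearly (±4 weeks) until growth-plate fusion, in line with Section 4.5.10. If the sponsor does want the right-hand image, it should state the purpose, amend Section 4.5.10 to match and add the image at baseline, so that sites, ethics committees and families see a single instruction. The recommended change costs one footnote in the next amendment and requires no change to any analysis.

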### Appendix 3 Low-Contrast Visual Acuity

A measure of high-contrast visual acuity will be performed using the Early Treatment Diabetic Retinopathy Study (ETDRS) charts and the low-contrast visual acuity test will be performed using the Sloan chart 2.5% contrast.

All charts will be provided for this study.

Patients should be placed at a distance of 2 meters from each chart during the examination.

The same settings (i.e., same charts and same distance) must be used at each examination.

For consistency, it is recommended the same examiner perform the tests at each visit for the same patient.

Both monocular (right eye, then left eye) and binocular (right and left eyes) testing should be performed using each chart wall-mounted at a distance of 2 meters, as follows:

• The right eye will be tested on the high–contrast ETDRS chart, followed by the left eye, then both eyes, and then move to the 2.5% low-contrast Sloan chart following the same sequence.

These charts are scored by the number of letters read correctly (out of 70), and numbers will be entered on the visual acuity evaluation forms provided, which will serve as a source document before being entered on the electronic case report form.

### Appendix 4 Telephone Interview

The purpose of this interview is to identify and collect information on any changes in the patient's health status (i.e., new or worsening neurological symptoms, signs of infection, any unusual signs or symptoms since patient left the clinic after the infusion) that warrant an unscheduled visit.

The telephone interview will be conducted by site personnel familiar with the patient(s) within 24 hours after completion of each infusion of ocrelizumab, and every 4 weeks between the study visits (with exemption of patients in the prolonged B-cell Monitoring Period without alternative treatment for MS when telephone interviews need to be performed every 12 weeks). The date of the telephone interview, or if the site was unable to contact the patient, will be recorded on the electronic case report form.

This form should be used and kept with the patient's records.

Please ask the following questions during the Telephone Interview. Read aloud and record patient's answers to the following questions:

1. Since your last visit or telephone interview, have you had any new or worsening medical problems that have persisted more than 1 day such as (select Yes or No):

1a)	Sudden changes in your thinking	🛛 Yes	🛛 No
1b)	Alterations in your behavior	🛛 Yes	🛛 No
1c)	Visual disturbances	🛛 Yes	🛛 No
1d)	Extremity weakness	🛛 Yes	🛛 No
1e)	Limb coordination problems	🛛 Yes	🛛 No
1f)	Gait abnormalities	🛛 Yes	🛛 No
1g)	Any other symptoms If yes, specify	☐ Yes	🗆 No

2. Since your last visit or telephone interview, have you noticed any of the following signs of an infection such as (select Yes or No):

2a)	Fever	🛛 Yes	🛛 No
2b)	Sweat	□ Yes	🛛 No
2c)	Chills	□ Yes	🛛 No
2d)	Low body temperature	□ Yes	🛛 No
2e)	Peeing less than normal	□ Yes	🛛 No
2f)	Rapid pulse	□ Yes	🛛 No
2g)	Rapid breathing	□ Yes	🛛 No

Ocrelizumab—F. Hoffmann-La Roche Ltd 154/Protocol WA39085, Version 10

